1) Abstract of the study

This protocol describes activities that are a part of a clinical trial grant (U01) application by the investigators to the National Institute of Dental and Craniofacial Research (NIDCR) examining an internet-based cognitive-behavioral treatment (I-CBT) for patients of the Temple University Kornberg School of Dentistry (TUKSoD) who suffer from significant dental anxiety. This is a 5-year clinical trial that will evaluate the efficacy of a brief I-CBT for the treatment of impairing dental anxiety among those seeking dental care at the clinics of TUKSoD.

The study will be a randomized controlled trial in which patients seeking services at the TUKSoD Faculty Practice Clinic who screen positive for dental anxiety will be provided with I-CBT under the supervision of psychology clinicians highly trained in CBT techniques versus dental assistants with minimal training designed specifically to prepare them to supervise the delivery of the I-CBT protocol to anxious dental patients. Patients (N=550) will be randomized to one of these two arms of the study or to a third (control) arm in which participants will be asked to view a video of nature scenes for a period of time equivalent to the dental anxiety intervention. The dental care provider for all participants will also be informed of their scores on the dental anxiety screening measure. Demonstration of relatively equivalent efficacy of the I-CBT treatment when provided by dental assistants versus more highly trained psychology personnel will facilitate the dissemination of I-CBT for dental anxiety to dental offices in a sustainable way that would allow greater access for a larger number of potential patients with dental anxiety.

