Initial assessments will be conducted in the few weeks preceding patients' already-scheduled appointments for dental treatment at TUKSoD. Patients meeting inclusion and exclusion criteria will then be offered I-CBT or the control intervention, to occur immediately prior to their scheduled dental treatment appointment. Efficacy based on primary outcome measures (e.g., reduction from baseline on self-rated and clinician-rated measures of dental anxiety/fear) and secondary outcome measures will be examined at assessments one and three months thereafter. Some additional interview ratings will be gathered from patients after they complete the dental anxiety intervention and after they complete the pursuant dental treatment appointment, and one brief questionnaire will be administered six and twelve months later. Finally, we will examine the impact that the intervention may have on attendance at scheduled dental appointments over the next 12 months.

2) Protocol Title

Efficacy of an Internet-based intervention for dental anxiety

3) Investigators

Page 1 of 28 Revision: May 12, 2023

[name], Associate Professor, Chair, and Residency Director, Pediatric Dentistry and Community Oral Health Sciences, Maurice H. Kornberg School of Dentistry, Temple University

[name], Assistant Professor, Department of Oral Health Sciences, Maurice H. Kornberg School of Dentistry, Temple University

4) Objectives

The primary goal of human subjects activities described in this protocol is to evaluate the efficacy of the Internet-based intervention for dental anxiety among patients presenting to the participating clinic(s). To achieve this overall goal, we propose 3 primary objectives:

Objective 1: We will compare the efficacy of I-CBT as administered by personnel with training and experience in CBT to the efficacy of the intervention as administered by dental assistants who have undergone a brief but specific training in the administration of the intervention, a goal which would allow the greater dissemination of this intervention. We will also examine within-group reduction of anxiety at assessments one and three months after the administration of the intervention.

Objective 2: We will compare the efficacy of the intervention, administered either by CBT personnel or dental staff, to an active control condition, the viewing of the control video and the notification of the dental provider of the patient's score on a measure of dental anxiety before the dental appointment.

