We propose general statistical analyses and sample size considerations for the U01 trial. Initial analyses will be conducted to determine normality of distributions of the continuous variables, and any necessary transformations will be conducted. Primary outcomes will be the MDAS (score ranging from 5 to 25) and the rating of fear of dental procedures from the ADIS-5 (0=no fear to 8=very severe fear). All eligible patients will be randomly assigned to one of the three conditions described above. Although randomization should provide relatively comparable groups, demographic variables that differ between groups and are correlated with the primary outcomes will be used as covariates. Patients will receive a full battery assessment of outcome measures at baseline and 1 and 3 months after the day of their index dental appointment (as well as assessments on the day of their index dental appointment).

Page 16 of 28 Revision: May 12, 2023

Preliminary statistical analysis will include measures of central tendency and dispersion, as well as an examination of the bivariate relationships among the primary and secondary outcome variables (e.g., client satisfaction, blood-injury-injection phobia), potential moderators (e.g., distress tolerance and pain sensitivity), and demographic characteristics.

Differences between the groups on baseline demographic, clinical and psychological measures will be examined using χ^2 (Pearson) or Student's *t*-tests, as appropriate. Moreover, differences on the variables listed above among completers and drop-outs will also be explored. Both per protocol and intention to treat (ITT) analyses will then be conducted.

Specific Aim 1

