Aim 1 will test the equivalence hypothesis (Ho: the two intervention conditions are not equivalent). MDAS and ADIS fear scores will be the primary outcomes to be compared between two intervention conditions for equivalence. The two one-sided tests (TOST) procedure of Schuirmann (1987) will be used to conduct the equivalence test. Linear mixed-effects models for repeated measures will be used to assess differences between intervention groups using the MDAS and ADIS fear rating as continuous outcome variables. Linear mixed-effects models will also investigate the treatment effect on dental anxiety or fear after accounting for other confounding factors. Similar analyses will be conducted for secondary outcome measures (pain sensitivity index, anxiety sensitivity index, sleep disturbance and sleep-related impairment scales, disability scale, distress tolerance scale, client satisfaction and blood-injury-injection phobia). Statistical significance will be set at p < 0.05. Multiple imputation (MI) will be used to handle missing follow-up data as described below.

Aim 1 will also determine whether the Internet-based intervention reduces dental anxiety/fear as determined by self-ratings or assessor ratings at one month and three months post-intervention. Initially, we will assess within-group change of anxiety or fear scores for each condition separately using paired *t*-tests. Linear mixed-effects models will be used to estimate within-group reduction of anxiety/fear at assessments one and three months after the administration of the intervention adjusting for other covariates.

Specific Aim 2

Aim 2 will assess the superiority hypothesis (Ho: there are no significant differences between the interventions and control). MDAS and ADIS-5 fear scores will be the primary outcomes to be compared. Initially, we will assess the differences between the interventions and control using two-sample *t*-tests. The main analysis will be based on linear mixed-effects models for repeated measures (using the MDAS score and ADIS-5 fear rating as continuous outcome variables) to assess differences between intervention and control groups. Linear mixed models will also investigate the treatment effect on dental anxiety or fear after accounting for other confounding factors. Similar analyses will be conducted for secondary outcome measures (e.g., client satisfaction and blood-

Page 17 of 28 Revision: May 12, 2023

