injury-injection phobia). Statistical significance will be set at p < .05. MI will be used to handle missing follow-up data as described below.

Specific Aim 3

Aim 3 examines the impact of the intervention on attendance at scheduled dental appointments over the following 12-month period to determine whether the intervention affects avoidance of dental procedures. First, we will examine whether the overall attendance rate is changed from pre- to post-intervention using a one-sample Chisquare test comparing the 12-month periods immediately before and immediately after the delivery of the intervention. The two intervention groups combined will be used for this analysis. We will also use a Chi-square test to compare post-intervention attendance rates between the two intervention groups. We expect the attendance rates will be similar for the two groups. Finally, we will conduct logistic regression analyses predicting attendance/nonattendance among intervention patients who did or did not demonstrate reduction in dental anxiety at 3-month follow-up. Relevant demographic characteristics and other potential confounding variables or moderators will be included in the final logistic models.

Missing Data

MI will be used to handle missing follow-up data when conducting ITT analysis for Specific Aims 1 and 2. There will be three steps in the MI procedure: 1) The missing follow-up data will be filled in 100 times to generate 100 complete datasets; 2) The 100 datasets will be analyzed by analyses of covariance with follow up scores at 1-month or 3-month as outcomes and treatment groups as the independent variable (Tr1 vs. Tr2 for Specific Aim 1, or Tr1 + Tr2 vs. AC for Specific Aim 2), controlling for baseline scores; 3) The results from the 100 complete datasets will be combined for the MI inference (Rubin 1987). SAS PROC MI and PROC MIANALYZE will be used for multiple imputation analysis using SAS 9.4 (SAS Institute Inc., Cary, NC, USA).

Analysis of Secondary Objectives

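### No dental-assistant versus control test is specified and the equivalence test has no margin, so a wide margin could credit a dental-assistant arm that has no effect

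*Combined protocol and SAP*

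**What the plan says.** The Abstract (section 1) states the purpose: "Demonstration of relatively equivalent efficacy of the I-CBT treatment when provided by dental assistants", compared with psychology personnel, is to open the way to dissemination in dental offices. About 550 patients are split roughly evenly over three arms.

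- **Aim 1 (section 8(c), Specific Aim 1).** "The two one-sided tests (TOST) procedure of Schuirmann (1987) will be used to conduct the equivalence test". MDAS and the ADIS-5 fear rating are both primary. No margin is given for either.
- **Aim 2.** Objective 2 (section 4) reads: "We will compare the efficacy of the intervention, administered either by CBT personnel or dental staff, to an active control condition". Under Specific Aim 2 the main analysis is a mixed model "to assess differences between intervention and control groups". Neither sentence says whether the I-CBT arms are pooled or tested one at a time. The contrast is written out only under Missing Data, in the imputation ANCOVA: "Tr1 + Tr2 vs. AC for Specific Aim 2", "controlling for baseline scores".
- **Analyses per arm.** "Initially, we will assess within-group change of anxiety or fear scores for each condition separately using paired" t-tests, followed by mixed models of within-group reduction. Neither involves the control arm.
- **Sample size.** Planned Analyses opens with "We propose general statistical analyses and sample size considerations for the U01 trial", but no effect size, SD, power, margin or dropout rate follows.

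**The concern.** Support for dental-assistant delivery needs evidence that this arm does something beyond control. As written, that evidence can only be indirect: the pooled arms beat control, and the two I-CBT arms are declared equivalent. The inference is sound only if the equivalence margin is smaller than the effect being preserved. With no margin stated, the plan does not exclude a wide one, or one chosen after outcomes are known. An effective psychology arm could then carry the pooled contrast while an ineffective dental-assistant arm passes as equivalent.

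The per-arm pre/post analyses do not close the gap. Patients enter on a high MDAS score, so scores may fall in any arm through regression to the mean.

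**Working it through.** The plan gives no power calculation to reproduce, so what follows is an illustration in SD units.

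**From the plan:** N = 550 in three roughly equal arms, so 550/3 = 183.3 per arm; significance at 0.05.

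**Assumed:** psychology effect over control 0.4 SD; dental-assistant effect 0; superiority two-sided at 0.05; each one-sided TOST at 0.05; normal approximation; one outcome at one time point.

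1. Standard errors. Arm versus arm: sqrt(2/183.3) = 0.1044. Pooled versus control: sqrt(1.5/183.3) = 0.0905.
2. Pooled superiority. The true pooled difference is (0.4 + 0)/2 = 0.2, so power = Phi(0.2/0.0905 − 1.96) = 59.9%, although one arm does nothing.
3. False equivalence at margin m: Phi((m − 0.4)/0.1044 − 1.645). It equals 5% at m = 0.4 and exceeds 5% only above that, that is, only when the margin is larger than the psychology arm's effect.
4. Both pass. With equal arms, the pooled contrast and the psychology-minus-dental-assistant difference are uncorrelated, so the joint probability is the product of steps 2 and 3. Simulation agrees.
5. Add the requirement that dental-assistant versus control is significant in the right direction. With a true effect of zero this happens in 2.5% of trials, which caps the joint pass whatever the margin.

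| Margin (SD) | TOST passes | Pooled and TOST | Same, 20% loss | Same, baseline-adjusted (r = 0.5, no loss) | Pooled, TOST and dental-assistant vs control (unadjusted, no loss) |
|---|---|---|---|---|---|
| 0.3 | 0.5% | 0.3% | 0.3% | 0.2% | 0.1% |
| 0.4 | 5.0% | 3.0% | 2.5% | 3.6% | 0.7% |
| 0.5 | 24.6% | 15% | 11% | 21% | 1.8% |
| 0.6 | 60.6% | 36% | 27% | 52% | 2.4% |

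6. Sensitivity to the psychology effect (unadjusted, no loss), pooled and TOST both passing at margins 0.5 and 0.6: 23% and 34% for an effect of 0.3; 4% and 19% for 0.5; 0.4% and 4.6% for 0.6; at most 0.02% for 0.8.
7. If neither arm works, the pooled test alone limits the joint pass to 2.5%.
8. The 2.5% cap in step 5 is per outcome and time. If any one of the four results (MDAS or ADIS-5 fear, 1 or 3 months) could carry the claim, the rate with the added requirement reaches about 7% at a 0.6 SD margin (assumed correlations 0.6 between outcomes, 0.7 between times).
9. Margin the trial can support. 80% TOST power at zero true difference needs (1.645 + 1.282) × 0.1044 = 0.306 SD. With 20% loss (146.7 per arm) it is 0.342. Multiplying by sqrt(1 − r²) for baseline adjustment gives 0.280, 0.265 and 0.245 for r = 0.4, 0.5 and 0.6 (0.31 to 0.27 with 20% loss).

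**The case against.** The strongest reply is that the missing margin does the damage, not the pooling. At margins this sample can power (about 0.31 SD unadjusted, 0.34 with 20% loss, 0.26 with r = 0.5), the worst joint false pass over all psychology effects from 0 to 1 SD is between 5% and 6% even without the arm-specific test. In the scenario above, that test moves the rate at a 0.3 SD margin only from 0.3% to 0.1%. This stands: a well-justified narrow margin removes most of the risk for a single outcome and time.

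Second, a zero dental-assistant effect beside 0.4 SD in the psychology arm is an extreme case. Both arms use the same online programme, and section 5 reports planning-grant findings that suggest equal efficacy. The 15% and 36% are therefore one selected scenario, and step 6 shows how far they move. Even so, whether the intervention works in dental assistants' hands is the question the trial asks, so the analysis should not presume the answer.

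Third, the pooled contrast appears only in the imputation step. The Aim 2 and Objective 2 wording, and the section 5 statement that I-CBT given by both types of personnel will be compared with control, could be read as allowing arm-specific tests. This also stands: the fault is non-specification, not exclusion. But an optional contrast can be reported selectively, and a pre-specified one cannot.

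**Conclusion.** The concern holds as a conditional risk that is cheap to remove. The plan specifies no controlled test of the dental-assistant arm and gives no TOST margin. If that arm had no effect, false equivalence would exceed 5% only with a margin larger than the psychology arm's effect, and nothing in the plan rules out such a margin. For an assumed psychology effect of 0.4 SD, the joint false pass is 3% at a margin equal to that effect and 36% at 0.6 SD. Adding the arm-specific test caps it at 2.5% per outcome and time. The missing contrast and margin are facts of the text. The percentages rest on assumed effects, margins and correlations, because the documents give none.

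**What to change.** 1. Keep the pooled contrast. Pre-specify dental-assistant versus control from the same mixed model and from the multiple-imputation ANCOVA.
2. Claim support for dental-assistant delivery only if that contrast is significant and TOST passes.
3. Fix a margin in points for MDAS and for ADIS-5 fear, each smaller than the I-CBT-minus-control effect to be preserved, with its justification and the TOST alpha. The sponsor must supply the effect sizes and SDs. Check each margin against the feasibility figures above.
4. State the testing order over two outcomes and two follow-ups, for example one named primary time point with MDAS before ADIS-5 fear.
5. Do this before arm-level outcomes are seen. The revision is dated May 2023 and completion was hoped for by July 31, 2023, so if outcomes have already been seen, disclose when each rule was set.

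This changes SAP wording only and needs no new data or visits. The price is power for the dissemination claim. With equal true effects in both I-CBT arms and a 0.31 SD margin, the chance of a full pass falls as follows:

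| True effect, both arms (SD) | Pooled and TOST | With added test |
|---|---|---|
| 0.2 | 49% | 38% |
| 0.25 | 64% | 54% |
| 0.3 | 74% | 68% |
| 0.4 | 81% | 80% |

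With 20% loss and a 0.34 margin it falls from 67% to 58% at 0.3 SD, and from 78% to 75% at 0.4 SD. With baseline adjustment (r = 0.5, margin 0.26) it falls from 76% to 72% at 0.3 SD. Ordering the four results costs some further power, which is not computed here.

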basic training in the nature and use of cognitive coping skills. (3) The third video was filmed from the perspective of a patient in the dental chair and provides additional and more intensive exposure to the feared dental procedure. The voiceover is a "dialogue" between the acting patient in the video, who presents cognitive coping from a self-administered/self-help perspective, and the participating patient, who is led through the steps to develop coping thoughts to counter his/her own anxious thoughts. The intervention closes with a brief module providing additional motivational enhancement for attending future dental appointments. Upon completing the intervention, patients attend their scheduled dental appointment and are encouraged to use the skills they learned from the intervention to cope with any anxiety they experience during that appointment.

The computer-based intervention was piloted on a sample of six dental patients from the TUKSoD Clinics (Potter et al., 2016). All patients completed the experimental intervention and attended their appointment for dental care, and 5/6 were contacted and re-assessed after one month. Three patients demonstrated clinically significant reductions in dental anxiety, and the remainder demonstrated lesser improvements. We next conducted a randomized controlled trial of the experimental intervention in comparison to a waitlist control condition (N = 151; Tellez et al., 2015). The computer-based intervention resulted in greater declines in dental anxiety, and clinician ratings of dental fear and avoidance were also markedly reduced. Among those who met criteria for dental phobia at baseline, a larger percentage of treated patients no longer did so after the treatment interval than was the case for patients assigned to the waitlist condition. Patients who received this computerized dental anxiety intervention reported high levels of satisfaction (83% were "very satisfied").

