A post-baccalaureate study coordinator with a background in psychology or a related field will perform many important tasks for the U01 project. After appropriate training, the study coordinator will conduct the bulk of the initial telephone screening interviews. He/she will also conduct diagnostic interviews at baseline and one-month and three-month follow-up assessments and track attendance at scheduled dental appointments for the 12-month period following the dental anxiety intervention. He/she will also complete reliability ratings for diagnostic interviews conducted by other study staff, providing full coverage of this activity with the graduate student. The study coordinator will also be charged with the rating of treatment fidelity/adherence of a portion of the

Page 6 of 28 Revision: May 12, 2023

interventions completed during the U01 project. The study coordinator will also conduct a range of data entry and management activities.

The dental staff for the proposed U01 will be two or more part-time dental assistants or expanded function dental assistants as defined in the State of Pennsylvania working with [name] at TUKSoD (one full-time equivalent). They will be trained in the administration of the Internet-based dental anxiety intervention by a psychologist, postdoctoral fellow, or doctoral student highly trained in CBT and the specific online intervention, and they will administer the dental anxiety intervention to those patients randomly assigned to the arm of the trial in which the intervention is delivered by dental staff. They will also assist in the payment of study subjects and other day-to-day tasks when these activities cannot be performed by the post-baccalaureate study coordinator.

7) Prior Approvals

See attached letters of support from the Directors of the Faculty Practice Clinic and the Graduate Clinics of TUKSoD.

8) Study Design

a) Recruitment Methods

Approximately 550 patients will participate in this research, roughly evenly divided between the three arms of the study.

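### Aim 2 sets about 367 pooled I-CBT patients against about 183 controls, and no analysis of it allows for unequal arm variances, so its standard errors can be off in either direction

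*Combined protocol and SAP*

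**What the plan says.** Section 8(a), Recruitment Methods, gives the size and split: "Approximately 550 patients will participate in this research, roughly evenly divided between the three arms of the study".

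Section 8(c) then describes three analyses for Aim 2:

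- **t-test.** Under Specific Aim 2: "Initially, we will assess the differences between the interventions and control using two-sample" t-tests. The pooled or Welch form is not stated. Student's form is named only for the baseline comparisons under Planned Analyses.
- **Mixed model.** Also under Specific Aim 2: "The main analysis will be based on linear mixed-effects models for repeated measures". No covariance structure, arm-specific variance or robust standard error is given.
- **ANCOVA after multiple imputation.** Under Missing Data: "The 100 datasets will be analyzed by analyses of covariance with follow up scores at 1-month or 3-month as outcomes", adjusted for baseline, with the contrast written as "Tr1 + Tr2 vs. AC for Specific Aim 2".

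The significance rule for Aim 2 is "Statistical significance will be set at p < .05"; sidedness is not stated. Planned Analyses provides for normality checks, transformations and descriptive measures of dispersion. It does not tie any finding of unequal spread between arms to a choice of method.

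**The concern.** A standard error built on one common variance is protected against unequal arm variances when the two groups are the same size. It loses that protection when they are not. Pooling two of three equal arms makes Aim 2 a 2:1 comparison, so the protection that the Aim 1 comparison has by design is absent here.

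The standard ANCOVA carries the common-variance assumption. The other two analyses will carry it too if they are run at their usual defaults. Aim 2 is a primary superiority objective on both primary outcomes (MDAS and ADIS-5 fear). At stake are the p-values and confidence intervals for those comparisons. If I-CBT outcomes are more variable than control outcomes, the test is conservative and loses power. If they are less variable, intervals are too narrow.

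**Working it through.** **Inputs from the documents.** Total about 550, three roughly equal arms: 550/3 = 183.3 per arm, so the pooled I-CBT group is 2 × 183.3 = 366.7. I use nt = 367 and nc = 183. Alpha is 0.05. The plan gives no effect size, SD, power or dropout rate behind the 550, so that figure cannot be reproduced; only the split can.

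**Assumptions.** Two-sided test, no dropout, normal errors. The ratio r = SD(I-CBT)/SD(control) is varied because the documents give no SD for any arm. For the ANCOVA, the SD that matters is the residual SD after baseline adjustment.

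**Formulas**, with the control SD set to 1:

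- Pooled variance: sp² = [(nt − 1)r² + (nc − 1)] / (nt + nc − 2)
- Pooled SE = √[sp²(1/nt + 1/nc)]
- True SE = √(r²/nt + 1/nc)
- k = pooled SE / true SE
- Actual alpha = 2[1 − Φ(1.96k)]; coverage = 1 − alpha
- Power where a correct SE gives 80% = Φ(2.8016 − 1.96k), with 2.8016 = 1.9600 + 0.8416

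**r = 1.25.** sp² = (366 × 1.5625 + 182)/548 = 1.3757. Pooled SE = √(1.3757 × 0.0081893) = 0.1061. True SE = √(0.0042575 + 0.0054645) = 0.0986. k = 1.076.

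**r = 0.8.** sp² = (366 × 0.64 + 182)/548 = 0.7596. Pooled SE = √(0.7596 × 0.0081893) = 0.0789. True SE = √(0.0017439 + 0.0054645) = 0.0849. k = 0.929.

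The last two columns below are the type I error of a simulated baseline-adjusted ANCOVA (20,000 runs per ratio, baseline slope 0.5), first with the ordinary SE and then with the HC3 robust SE.

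| r | k | Actual alpha | 95% CI coverage | Power (80% if SE correct) | Simulated alpha, ordinary SE | Simulated alpha, HC3 |
|---|---|---|---|---|---|---|
| 0.67 | 0.880 | 8.5% | 91.5% | – | 8.7% | 5.1% |
| 0.8 | 0.929 | 6.9% | 93.1% | – | 6.9% | 5.1% |
| 1.0 | 1.000 | 5.0% | 95.0% | 80.0% | 5.1% | 5.0% |
| 1.25 | 1.076 | 3.5% | 96.5% | 75.5% | 3.3% | 4.8% |
| 1.5 | 1.138 | 2.6% | 97.4% | 71.6% | 2.2% | 4.8% |

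No power is shown for r below 1, because the ordinary test then exceeds its nominal level. Formula and simulation agree to within about 0.4 percentage points.

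**Comparison with 1:1.** At 183 against 183, k = 1.000 for every ratio tried (0.5 to 2). The problem comes from the pooled 2:1 contrast and does not affect Aim 1 at equal arm sizes.

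**When does variable response matter?** Let the individual response have SD τ, in control-SD units, and correlation ρ with the score the patient would have had untreated. Then r = √(1 + τ² + 2ρτ).

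- ρ = 0: τ of 0.25, 0.5, 0.75 and 1.0 makes the pooled SE 1%, 4%, 8% and 12% too large.
- ρ = −0.5: τ = 0.5 gives r = 0.87, an SE 5% too small and alpha 6.2%; τ = 1.0 gives r = 1.00 and no error.

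So neither the size nor the direction of the error follows from the mere fact that patients respond differently.

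**The case against.** The strongest reply is that the plan does not commit Aim 2 to equal-variance methods. The t-test form is open, the main mixed model's covariance is open, and even for the ANCOVA equal variance is the standard form and not a stated choice. That stands. For the t-test and mixed model this is a gap in specification, not a wrong method. Analysts who look at dispersion, as planned, might also notice unequal spread; but nothing says what they would then do.

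Several stronger readings are tempting and are not supported:

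- **Variable response by itself makes the error bars wrong.** The plan does hypothesise that pain sensitivity and distress tolerance moderate efficacy. Moderation implies no particular variance ratio, and as shown above the error can vanish.
- **The pilot shows that spread will differ.** Section 5 reports "Three patients demonstrated clinically significant reductions in dental anxiety, and the remainder demonstrated lesser improvements". That was six patients with no control arm, so it carries no information on the ratio of I-CBT to control variance.
- **Pooling two provider types adds material spread.** A 0.3 SD difference in means between the two I-CBT arms changes the SE by only 0.4%, and the plan expects those arms to be equivalent.
- **Floor effects would inflate type I error.** Patients enter with high scores, so bunching at the floor in I-CBT alone would itself be a treatment effect. The null would be false and no type I error could occur.

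The calculation also has limits. It covers a two-sample comparison and a complete-data ANCOVA. The repeated-measures model and the imputation step were not simulated.

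**Conclusion.** The point holds as a gap in specification with a bounded consequence. Aim 2 is a 2:1 contrast; its ANCOVA in standard form, and its t-test and mixed model at their usual defaults, rest on a common variance; and nothing in the plan covers the case where the arms differ. The treatment estimate is not biased. Only its standard error, interval and p-value are affected.

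For SD ratios of 0.8 to 1.25, the standard error is about 7% too small to 8% too large, alpha about 6.9% to 3.5%, and coverage about 93% to 96.5%. Where a correct standard error would give 80% power, the pooled one gives about 75.5% at a ratio of 1.25. At a ratio of 1 there is no error. These ratios are assumptions, as are two-sided testing, no dropout and normal errors, and the documents do not show which side of 1 the ratio will fall.

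This is an inexpensive improvement to a primary-aim analysis, not a demonstrated error in it.

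**What to change.** In Section 8(c), under Specific Aim 2 and Missing Data, state for the Aim 2 contrast that:

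1. the ANCOVA in each imputed data set uses heteroscedasticity-robust standard errors (HC3, for example), and these are what is passed to the combining step;
2. the mixed model estimates residual variances separately by arm (in SAS, the GROUP= option);
3. the two-sample t-test is the Welch form.

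The cost is two or three sentences and one option per model. Little is lost if the variances turn out equal: at a ratio of 1 the simulated type I error with robust standard errors is 5.0%, and over ratios of 0.67 to 1.5 it stays between 4.8% and 5.1%. Fixing the choice before outcomes are compared by arm also removes a later choice between competing standard errors.
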